Title of Study: A Prospective, Randomized, Double-Blinded, Placebo-Controlled Trial of DaxibotulinumtoxinA for Injection for the Management of Plantar Fasciitis

Study Type: Phase 2

Study Center(s): Up to 2

Study Design: Prospective, double-blinded, randomized, placebo-controlled clinical trial

[REDACTED]

[REDACTED]

Objective: The specific aim of the study is to compare the safety and efficacy of a single administration of DaxibotulinumtoxinA for Injection versus placebo for managing plantar fasciitis

Study Population: Male and female adult subjects who have plantar fasciitis that has not responded to conservative treatment modalities

[REDACTED]

[REDACTED]

[REDACTED]

[REDACTED]

[REDACTED]

Number of Subjects: Sixty subjects (60) will be randomly assigned to one of two study groups:

- Group 1 subjects (n=30) will receive active daxibotulinumtoxinA injections
- Group 2 subjects (n=30) will receive placebo vehicle-only injections.

Duration of Study: Total length of time required to complete study: 6–12 months.

Total length of subject follow-up: 4 months.

Inclusion criteria:

1. Written informed consent, including authorization to release health information
2. Skeletally mature, male or female patients 18 to 65 years of age with diagnosis of unilateral plantar fasciitis by physical examination and/or ultrasonography
3. Unilateral plantar fasciitis as defined as no symptoms or signs in the contralateral foot with no sought medical attention in the contralateral foot
4. Persistent heel pain for more than three months

[REDACTED]

[REDACTED]

[REDACTED]

Exclusion criteria:

1. No previous injections of botulinum toxins
2. Entrapment of the posterior tibial, lateral plantar, or medial plantar nerve (local nerve entrapment)
3. Fixed hindfoot varus
4. Posterior tibial tendon dysfunction
5. Severe pes planus
6. Midfoot collapse
7. Significant talar or navicular callus
8. Tarsal coalition or rigid flatfoot
9. Systemic disease associated with foot pain
10. Sciatica
11. Severe osteoarthritis of the forefoot, midfoot, or ankle
12. Aminoglycoside therapy
13. Peripheral vascular disease
14. Rheumatoid arthritis
15. Poorly controlled diabetes mellitus (hemoglobin A1C greater than 8%)
16. Previous surgery on the midfoot or hindfoot
17. Spasticity
18. Neuromuscular disease
19. Systemic muscle weakness
20. Fibromyalgia
21. Allergy or sensitivity to any components of the study treatments
22. Comorbidities that confound the evaluation of the feet

[REDACTED]

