22. Comorbidities that confound the evaluation of the feet

[REDACTED]

[REDACTED]

[REDACTED]

[REDACTED]

[REDACTED]

[REDACTED]

[REDACTED]

[REDACTED]

Deviation from **any** entry criterion excludes a subject from enrollment into the study.

Informed Consent

If a subject meets the study entry criteria, the study will be presented to them. A thorough explanation of the study will be provided to the patient, and adequate time will be allowed to ask questions about potential study participation.

[REDACTED] Once the patient has been fully informed, they will be asked to sign the IRB approved study consent form and become a study subject.

The informed consent document will adhere to the ethical principles stated in the Declaration of Helsinki and will include the elements required by FDA regulations in 21 CFR Part 50, as well as the elements required by the International Conference on Harmonisation (ICH) Good Clinical Practice (GCP) guideline, and applicable federal and local regulatory requirements. The consent form must also include a statement that the sponsor, their designees, and auditing regulatory agencies will have direct access to the subject's records and medical history for study related purposes.

The subject will be given a copy of the signed informed consent document with the original kept on file by the Investigator. All of the above activities must be completed before any study related procedures are conducted (including any screening study procedures).

[REDACTED]

[REDACTED]

[REDACTED]

[REDACTED]

Sample Size Estimate

The clinical trial is designed to evaluate the safety and efficacy of DaxibotulinumtoxinA for Injection for the management of plantar fasciitis. Based upon published peer review trials, 60 subjects will be enrolled.

[REDACTED]

[REDACTED]

[REDACTED]

[REDACTED]

[REDACTED]

[REDACTED]

[REDACTED]

[REDACTED]

[REDACTED]

Study Procedures/Study Interventions

All clinical laboratory assessments will be conducted locally at the clinical site facilities.

Screening: Subjects presenting with heel pain will be examined to verify the diagnosis of plantar fasciitis. Then, subjects with plantar fasciitis will be screened to determine if they meet the study eligibility criteria. Prospective study participants will be informed of the study, and the requirements for study participation will be explained to them. [REDACTED]

In addition, they will undergo an examination of both feet. [REDACTED]

[REDACTED]

[REDACTED]

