[REDACTED]

Injection Visit: After consent and randomization, Vital signs [Blood Pressure (BP), Heart Rate (HR), Pulse and Temperature] are taken prior to and following study drug administration. [REDACTED]

[REDACTED]

[REDACTED]

[REDACTED]

[REDACTED]

Follow-up: [REDACTED]

Acceptable study visit windows can be ± 3 days. [REDACTED]

[REDACTED]

Outcome Measures***Primary safety endpoint***

- Adverse events associated with the two study treatments

Primary outcome measure

- Improvement in the American Orthopaedic Foot and Ankle Score (AOFAS)

[REDACTED]

American Orthopaedic Foot and Ankle Score (AOFAS)

The American Academy of Orthopaedic Surgeons developed several musculoskeletal outcomes instruments to collect patient based data to use to assess the effectiveness of treatments and to study the clinical outcomes of the treatments. The AOFAS foot and ankle questionnaire was designed for use in patients 18 years old and older. This questionnaire documents patient assessments of foot and ankle conditions and improvements resulting from treatments. Disability indices for the lower limb core, global foot and ankle function, and shoe comfort can be evaluated using this instrument. The questionnaire requires about 10 minutes to complete.

[REDACTED]

[REDACTED]

[REDACTED]

[REDACTED]

[REDACTED]

[REDACTED]

[REDACTED]

[REDACTED]

Study Discontinuation

Screen failures: A screen failure occurs when a subject for whom informed consent is obtained: 1) does not meet inclusion/exclusion criteria, 2) the study randomization was not completed, or 3) the subject withdraws consent for study participation.

Subject discontinuation: Study participants may end their study participation at any time for any reason. When subjects withdraw from the study, the reason for their discontinuation will be documented. Subjects who end their study participation early will not be replaced, and the reason for their study discontinuation will be documented.

Subjects who do not complete the study who cannot be contacted and have no reason for their discontinuation will be classified as “lost to follow up.” Three attempts will be made to contact the subjects by phone or email. If the subject cannot be reached, then certified mail will be used to contact them.

Adverse Events (AE)

The study will evaluate and document any adverse events associated with the use of the injectable botulinum toxin or placebo used in the clinical trial.

[figure not shown]

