- Life-threatening, (i.e., the subject was, in the opinion of the Investigator, at immediate risk of death from the event as it occurred. It does not apply to an AE that hypothetically might have caused death if it were more severe)
- Persistent or significant disability/incapacity (i.e., the AE results in a substantial disruption of the subject's ability to carry out normal life functions)
- Requires in-patient hospitalization or prolongs hospitalization (i.e., the AE required at least a 24 hour in-patient hospitalization or prolonged a hospitalization beyond the expected length of stay. Hospitalizations for elective medical/surgical procedures, scheduled treatments, or routine check-ups are not SAEs by this criterion).

Any AE experienced by a study participant whether or not it is considered to be related to the study protocol will be documented. An AE can include subjective symptoms and/or objective findings. All AEs that occur during the study will be reported on study-specific case report forms and in the subject's electronic medical record. All AEs will be graded according to their severity (mild, moderate or severe).

Any AE that is associated with subject termination from the study protocol will be reported to the sponsor and our IRB within seven days of learning about the AE.

The investigator also will document their opinion as to whether the AE was related to the study product according to the following classification: 1) unrelated, 2) possibly related, 3) probably related, and 4) definitely related.

[figure not shown]
Study participants who have experienced an AE will be followed until the AE is resolved, the subject is lost to follow-up, or the AE is explained or stabilized.

All serious AEs will be reported immediately (within 48 hours) to the study sponsor and the IRB using a SAE form. The sponsor then will report the SAE to the medical monitor for the study. The SAE form will include the nature of the SAE, the time of onset relative to the use of the product, the duration and severity of the event, and whether or not the study was interrupted or the participant was discontinued as a result of the SAE.

Data Analysis

Data analysis will only be conducted on outcomes from subjects who were dosed.

Study data will be analyzed according to each subject's randomization assignment. All evaluable data will be included in the analysis following the intent-to-treat principle. The primary analysis will focus on the improvement in the AOFAS.

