[figure not shown]

Data Management

The Department of Orthopaedic Surgery at Wake Forest School of Medicine will be responsible for data collection and data management.

Data Collection

All study data will be collected on approved case report forms (CRF). The data will be entered into a REDCap database that meets all HIPPA requirements, is backed up every 24 hours, and is located behind a firewall. Information that can be used to support the data collected on CRF's will be readily available to verify CRF entries.

Compliance with study protocol: The research coordinator will monitor the study participant compliance with the treatment protocols. Any deviations from the assigned treatment group or the actual treatment received by any study participant will be documented. Completion of follow-up visits also will be monitored. Subjects who miss study visits will be contacted and their visits rescheduled.

Study database: Expertise on study design, biostatistical analysis, and information management will be coordinated with the assistance of computer programmers and biostatisticians from the Department of Public Health Sciences at the Wake Forest School of Medicine.

Treatment of Missing data: Some data elements will be missing in this study due to subjects who withdraw from the study, subjects who are lost to follow-up, or subjects who do not complete all study visits. The completion status of each subject will be documented (e.g., completed protocol, withdrew from study, lost to follow-up, etc.). Data from subjects for whom all study data is not complete will be included in the data analysis up until the time of

their withdrawal from the protocol. All reasonable efforts will be made by the study staff to maintain contact with the study participants during their participation in the study. The study coordinator will attempt to contact any subjects who are lost to follow-up. For subjects who are unwilling to return to clinic for follow-up, the study coordinator will attempt to contact them and to collect study data from them during a telephone call or by forms sent to them through the mail.

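### The visible analysis rule groups all study data by randomised arm, with no exception for the primary safety endpoint, so a dosing error would put adverse events under a treatment not given

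*Combined protocol and SAP*

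**What the plan says.** The grouping rule appears in the synopsis (Statistical Methods) and again in the Data Analysis section: "Study data will be analyzed according to each subject's randomization assignment". In both places the next sentence is "All evaluable data will be included in the analysis following the intent-to-treat principle", followed by a statement that the primary analysis concerns AOFAS improvement. The Data Analysis section also sets the population: "Data analysis will only be conducted on outcomes from subjects who were dosed".

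The synopsis and the Outcome Measures section give the primary safety endpoint as "Adverse events associated with the two study treatments".

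Under Data Collection, in the item on compliance with the protocol, the plan provides that "Any deviations from the assigned treatment group or the actual treatment received by any study participant will be documented". The visible text does not say how that record enters any analysis.

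**The concern.** Grouping by assignment protects the randomised comparison of AOFAS. A safety summary has a different purpose: it describes what happened to people exposed to each product. The protocol frames AEs that way itself. Its definition starts from administration of the investigational product, and the investigator judges relatedness to the study product.

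Under the visible rule, a subject randomised to placebo but injected with toxin is dosed, so is analysed, and is counted in the placebo column. Any toxin reaction in that subject then raises the placebo AE rate. An error in the other direction adds a placebo-exposed subject to the toxin column. Both tend to narrow a real toxin-placebo difference, which is the non-conservative direction for safety. The plan anticipates such deviations by requiring a record of them, but the stated rule does not use that record.

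**Working it through.** **Does the rule reach adverse events?** The sentence does not name safety, so its scope has to be read from the rest of the document.
- Data Collection says that all study data go on case report forms.
- The Adverse Events section says that AEs go on study-specific case report forms.
- AEs are the primary safety endpoint.
- No visible sentence limits the rule to efficacy, defines a separate safety set or groups AEs by treatment received.

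On the visible text, AEs are study data and fall under the rule.

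**Inputs.** The synopsis gives the arm sizes: "Group 1 subjects (n=30) will receive active daxibotulinumtoxinA injections" and "Group 2 subjects (n=30) will receive placebo vehicle-only injections". The visible text gives no expected AE rate and no dosing-error rate, so the rates and counts below are assumptions. The plan has no figure of its own on this point to reproduce.

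**Common events, assumed AE rates 30% (toxin) and 10% (placebo).** The true difference is 20.0 points.
- Two placebo subjects given toxin: placebo rate as randomised = (28 × 0.10 + 2 × 0.30)/30 = 3.4/30 = 11.3%. Difference = 30.0 − 11.3 = 18.7 points.
- Two swaps in each direction: toxin rate as randomised = (28 × 0.30 + 2 × 0.10)/30 = 8.6/30 = 28.7%, with placebo again at 11.3%. Difference = 17.3 points.
- Standard error of the difference at 30 per arm = √(0.3 × 0.7/30 + 0.1 × 0.9/30) = √0.010 = 10 points.
- The shifts of 1.3 and 2.7 points are therefore about 0.13 and 0.27 standard errors.

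**Rare events.** One misplaced event moves 1/30 = 3.3 points of incidence into the wrong arm. The cases below assume that one subject randomised to placebo receives toxin and has the event.

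| Other events | As randomised, toxin vs placebo | As treated, toxin vs placebo |
|---|---|---|
| None | 0/30 vs 1/30 (−3.3 points) | 1/31 vs 0/29 (+3.2 points) |
| 3 on toxin, 0 on placebo | 3/30 vs 1/30 (+6.7 points) | 4/31 vs 0/29 (+12.9 points) |

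In the first row the apparent direction reverses. Neither version of that row is statistically informative (Fisher's exact p = 1.0 both ways), so the reversal affects the descriptive table and not a test result.

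**How likely is an error?** With a per-subject error rate q, the chance of at least one error in 60 is 1 − (1 − q)^60. For assumed q of 0.5%, 1%, 2% and 5% this gives 26%, 45%, 70% and 95%. The documents support none of these rates. With no errors, the two groupings are identical.

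**The case against.** The case on the other side has five parts.

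- **Missing text.** A block not shown follows the Data Analysis text directly, and there are gaps in the AE and injection-site text. A safety-analysis rule could sit in any of them. This stands: a reader might infer that the plan has no safety-analysis rule, and the documents do not support that. They show only that the visible rule makes no exception. Any exception in the hidden text would still need reconciling with the unqualified sentence in two places.
- **Scope.** The sentence leads into intent-to-treat and AOFAS, so it may have been meant for efficacy only. That is a plausible intention, but the wording is unqualified and AEs are recorded as study data. Naming AOFAS as the focus of the primary analysis does not narrow the grouping rule.
- **Population.** Analysis is already limited to dosed subjects, so that part of a safety set exists. This stands, and only the grouping is at issue.
- **Size.** The harm needs a dosing error in a trial with a single administration, and for common events the shift is well inside sampling error. This stands. The rare-event figures also assume that the mis-dosed subject has the event.
- **Individual handling.** A reader might infer that one serious toxin event listed under placebo would by itself change the safety conclusion. The documents do not support that. Each serious event goes to the sponsor and IRB, and through the sponsor to the medical monitor, with its onset relative to product use. Every AE gets a relatedness judgement, and deviations in treatment received are recorded. The event would be traceable. What remains is that none of this decides which column of the summary table it is counted in.

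**Conclusion.** The point holds as a minor one. The rule as visible does not fit the primary safety endpoint: followed literally, it counts a mis-dosed subject's AEs under a treatment that subject did not receive. Under the assumed 30% and 10% rates the effect is 1.3 to 2.7 points, against a standard error of about 10. It matters mainly for a rare event, where one subject can turn the descriptive comparison round. It has no effect if every subject receives the assigned injection, and the documents give no reason to expect errors.

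Confidence is high that the visible text makes no safety exception. It does not extend to what the text not shown may contain.

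**What to change.** First check whether the text not shown already sets the grouping for safety. If it does not:

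- Limit the randomisation-assignment sentence to efficacy, in both the synopsis and the Data Analysis section.
- Add one sentence: AEs and injection-site findings are summarised in all dosed subjects, grouped by treatment actually received.

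If the hidden text does contain such a rule, only the first change is needed, so that the passages agree.

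The cost is one sentence and a qualifier in two places. The record of treatment received is already required, and the AOFAS grouping, sample size and trial conduct stay as they are. The change should be made before unblinding, so that the grouping is not chosen with a mis-dosed subject's events in view.
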